Within alloplastic reconstruction, the use of tissue expanders increases the use of opioid and non-opioid analgesia as compared to the immediate insertion of an implant.⁶ Predictive risk factors have been identified for developing chronic pain after breast surgery. Psychosocial and patient factors include baseline preoperative anxiety, depression, high BMI, younger age (<40), and catastrophizing.^{18,19} Surgical factors include severe acute post-operative pain, axillary surgery, and adjuvant radiotherapy.^{12,18} These studies underscore the importance of adequate perioperative pain management to reduce the risk of chronic pain in the setting of specific prognostic factors and to improve overall recovery.

Evidence-based multimodal perioperative management protocols improve the quality and value of care delivered for breast reconstruction patients.²⁰⁻²² These Enhanced Recovery After Surgery (ERAS) protocols have been applied to patients undergoing mastectomy with immediate alloplastic breast reconstruction and successfully demonstrate benefits of decreased opioid usage, decreased acute post-operative pain, same-day discharge, patient satisfaction, and well-being.^{20,21,23-25} In these published recommendations for optimal perioperative care, regional blocks of the chest are absent from the list of supported strategies due to lack of high-level evidence.^{15,20,21,26} Recent systematic reviews and anesthesia guidelines support regional blocks as an important

adjunctive strategy to these multimodal perioperative protocols for patients undergoing major oncologic breast surgery and breast reconstruction.²⁶⁻²⁸

Regional blocks of the chest have the potential to decrease acute and chronic pain but are absent from the list of supported strategies due to lack of high-level evidence.^{15,20,21,26} Recent meta-analysis, systematic reviews and anesthesia guidelines support regional blocks as an important adjunctive strategy to these multimodal perioperative protocols for patients undergoing major oncologic breast surgery and breast reconstruction.²⁶⁻²⁹

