The design of the pilot RCT is the same as the future definitive trial, a parallel-group, double-blinded randomized controlled trial (RCT). The target population are patients undergoing mastectomy with IBR using tissue expanders or immediate implants. The intervention will be a local anesthetic regional block defined as a TPVB with Pecs 1 (TPVB+) using local anesthetic infiltrate. The local anesthetic block (LA block) will be compared to a placebo block (sham block) using normal saline infiltrate. Thus, each patient in this study will be assigned to receive either; 1) LA Block: TPVB and Pecs I block with local anesthetic infiltrate, or 2) sham block: TPVB and Pecs I block with saline infiltrate. The assignment of intervention will be determined by randomization through REDCap. The pilot trial will be conducted at Mount Saint Joseph Hospital (MSJH).

Each participant will be assigned a consecutive Study ID at time of enrollment. Patients will be randomized 1:1 to either LA or sham block. Patients undergoing symmetrizing procedures as part of a bilateral breast surgery will not have a regional block on the symmetrizing side (which is not IBR). Patients undergoing bilateral IBR surgery using implants or expanders on both breasts will not be included in the study due to risk of local anesthetic toxicity with bilateral TPVB+.

The randomization sequence will be created using REDCap-generated 1:1 randomization with permuted blocks of varying size (4 and 6). The assignments (LA or sham) will be placed in order in opaque, consecutively numbered envelopes. The sequence and envelopes will be created by an independent research assistant who will not be involved in the remainder of the study implementation.

Study participants, Operating Room (OR) anesthesiologists, surgeons, research assistants, and nurses in the OR, Post-anesthesia Care Unit (PACU), and ward will be blinded as to whether a participant receives LA block or sham block. At MSJH, the anesthesiologists in the operative theater are separate from the team of regional anesthesiologists performing regional blocks in the preoperative area. Only the regional anesthesiologist and anesthesia assistant in the preoperative block area will be unblinded to reduce the potential unnecessary risk of a pneumothorax with the sham saline TPVB. This will enable injection of saline just outside of the paravertebral space.

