Preliminary evidence of efficacy: Although severe acute post-operative pain is not the only risk factor for chronic post-surgical pain (CPSP), an intervention that does not decrease postoperative pain is unlikely to have a significant impact on CPSP. If the 80%

confidence interval for the between-group difference in average pain score in the 24-hour postoperative period favours LA block, we will consider that preliminary evidence of efficacy.^{65,66}

Secondary outcomes of the pilot trial include adverse events related to study interventions. We will also collect the outcomes for the definitive trial to test and refine data collection processes.

The primary outcome in the definitive trial is chronic pain, defined by the Pain Burden Index, measured at 3 and 6 months following surgery. The Pain burden Index examines postsurgical pain in four postoperative body areas. The Index is calculated as a sum of the four locations (breast, chest, axilla, arm) multiplied by the frequency of pain¹² (see Form 8: Pain Burden Index).

Secondary outcomes of the definitive trial include:

- Opioid analgesia requirements during surgery and in the first 24 hours after surgery, defined as morphine milligram equivalents (MME). The total MME will include intraoperative opioids administered in the OR and postoperative opioids administered/ingested in the Postanesthetic Care Unit (PACU), Surgical Day Care Unit (SDC), Inpatient Unit, and home in the 24-hour period after completion of surgery. Opioids consumed will be converted to MME (see Appendix 3: Calculation of Morphine Milligram Equivalents (MME)).
- Acute patient-reported pain scores:
 - Numerical Rating Scale (NRS; 11-point scale) measured at the standard time points of nursing care assessments: preoperatively (baseline); four times per hour in PACU until discharge; if admitted, hourly for 2 hours, and then every 6 hours in the Inpatient Unit; and at discharge from hospital; 24 hours after surgery is complete.
- Opioid-induced side effects:
 - Postoperative nausea and vomiting
 - Nausea severity (by Verbal Rating Scale) in PACU
 - Vomiting episodes (0-48 hours after surgery) in PACU & home
- Quality of recovery (Form 7: Quality of Recovery-15 Questionnaire)

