 - Measured with the Quality of Recovery-15 (QoR-15) scores at baseline prior to surgery and 24 hours after surgery⁶⁷⁻⁶⁹. This 15-item questionnaire assesses patient-reported pain, physical comfort, physical independence, psychological support, and emotional state.⁶⁹ It takes an average of 2.5 minutes to complete. The QoR-15 has been statistically validated and is designed for both ambulatory and inpatient surgery populations.^{68,70}
- Length of stay (LOS) in hours in hospital

- Measured from the time admitted to PACU to the time discharged from hospital. LOS includes time in the PACU, Surgical Day Care (SDC) and, if required, Inpatient Unit. Patients are transferred between units and discharged from hospital according to standardized institutional criteria (see Appendix 4: PACU and SDC Discharge criteria).
- Time-based outcome measures:
 - time to perform ultrasound-guided TPVB+
 - time under general anesthesia
 - time in PACU
 - failure of discharge from PACU and requiring admission
- Rescue medications:
 - Need for rescue opioid analgesics and anti-emetics
 - Rescue medications are defined as those required “as needed” (ie, beyond scheduled) in the PACU, ward, and after discharge
 - Time to rescue opioid analgesics and anti-emetics
- Failure of early discharge:
 - Emergency room visits within 48 hours of discharge
- Complications and adverse events
 - Related to the ultrasound-guided regional block: vascular or nerve injury, Horner’s syndrome, bleeding/hematoma, local anesthetic systemic toxicity, pneumothorax, distortion tissue planes during axillary dissection, and other.
 - Related to the surgery: hematoma, tissue necrosis, urgent unplanned return to the operative theater within 24 hours of surgery.

These measures are listed in Form 6: Clinical Form and Form 11: Data Collection Form.

Sample Size

240 IBR procedures are performed annually at MSJH, 50% participation yields ~ 30 patients in 3 months. Assuming a difference of 1 and standard deviation of 1.2, this sample size yields > 80% probability that the lower bound will exclude 0.⁴⁵

Additional Details of Study Design

Participants will also be given at the time of consent a post operative package. This will contain the Quality of Recovery-15 Questionnaire (Form 7), Recovery Booklet (Form 5) and Pain Burden Index (Form 8).

The Quality of Recovery-15 Questionnaire (see Form 7) is to be completed at 24 hours after surgery in paper format or electronic format (based on their preference). This

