Participants in this study, as compared to those not receiving regional anesthesia, may have an additional risk of Local Anesthetic Systemic Toxicity (LAST, a serious adverse reaction to local anesthetic occurring in less than 1 in 12,000 cases⁷²), or other risks specific to the injection of local anesthetic.

Risk/benefit discussions with prospective participants will occur at the time of consent for the study and participants will also have the opportunity during the PAC call/visit and on day of surgery to ask the anesthesiologist questions regarding the regional block procedure. Participants may contact the research assistant at any time before their surgery date with questions regarding the regional block procedure. Questions beyond the scope or knowledge of the research assistant will be forwarded to the appropriate study physician with expertise in anesthesiology or surgery.

Assessment of Safety

The safety of the TPVB+ have been established in the literature. There are rare complications associated with the blocks which will be clearly defined and outlined to the

participant during the recruitment phase of the study. The participant will have two separate occasions to ask the medical team and trained anesthesiologist for details on the regional anesthesia: during the PAC visit/phone call and preoperatively on the day of surgery. The TPVB+ will be performed by a consistent group of trained regional anesthesiologists.

Adverse Events

Adverse events related to study interventions (TPVB+) will be recorded and tracked as per the study Data Collection Form on REDCap.

Statistical Analysis [\(back\)](#)

Patient characteristics and outcome measures will be summarized by group. An 80% confidence interval for the difference in average pain score over 24 hours will be calculated.

Quality Control and Assurance

All staff anticipated to be involved in the study, including anesthesiologists, general surgeons, plastic surgeons, research assistants, and nursing staff will be notified about the study and educated as appropriate on study interventions, data collection, and participant confidentiality. All staff providing study interventions (regional blocks), surgery, or perioperative care will be educated on relevant study outcomes being monitored.

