Participants will be randomly assigned to receive TPVB+ with local anesthetic or sham before general anesthesia. For all participants, data will be collected on the Intake Form, Clinical Form, Quality of Recovery-15 Questionnaire, Pain Burden Index, and Recovery Booklet in the following 7 sections:

1. The Intake Form will be completed by the patient during the initial contact phone call and includes information on general demographics and inclusion/exclusion criteria (without identifying information).
2. The first section of the Clinical Form will be used to record information on the perioperative course including the type of surgery performed: unilateral or bilateral; partial or total mastectomy with or without sentinel lymph node biopsy or axillary lymph node dissection; tissue expander or immediate implant reconstruction; adjunctive procedures will be recorded including biopsies and balancing reduction procedures.
3. The second section of the Clinical Form will record information on the general anesthesia provided; preoperative medications, intraoperative analgesics, sedatives, antiemetics, and anxiolytics. The form will also include details on the regional block and time to perform the block. Surgical and regional block complications within 24 hours of surgery will be recorded.
4. The third section of the Clinical Form will include information on participant-reported pain scores and medications in the postanesthetic care unit and inpatient ward.

5. The Quality of Recovery-15 Questionnaire will be completed by the participant at baseline before surgery and at 24 hours after surgery to evaluate the quality of their recovery.
6. The Recovery Booklet will be completed by the participant during the first 7 days after surgery to track scheduled and rescue medications required, opioid-related side effects (nausea and vomiting), and pain at 24 hours after surgery.
7. The Pain Burden Index will be completed by the participant 3 months and 6 months after surgery to evaluate for the presence and severity of chronic pain.

Confidentiality [\(back\)](#)

Management of Identifying Data:

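### The pilot's efficacy interval is stated and sized as a simple difference between arms, although preoperative NRS is collected and could be adjusted for at little risk

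*Protocol*

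**What the plan says.** In Outcome Measures, the protocol counts it as preliminary evidence of efficacy if the 80% "confidence interval for the between-group difference in average pain score in the 24-hour postoperative period favours LA block". The Statistical Analysis section adds that outcomes are summarised by group and that "An 80% confidence interval for the difference in average pain score over 24 hours will be calculated". The Sample Size section supports about 30 patients with "Assuming a difference of 1 and standard deviation of 1.2", and concludes that "this sample size yields > 80% probability that the lower bound will exclude 0". The SD is not described as residual or adjusted, and no correlation with a baseline value is given.

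The acute-pain item in Outcome Measures says that NRS is "measured at the standard time points of nursing care assessments: preoperatively (baseline") and then repeatedly after surgery. QoR-15 is collected before surgery and at 24 hours. Study Design describes 1:1 randomisation in permuted blocks of 4 and 6 and states no stratification.

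**The concern.** In a trial of about 30 patients, part of the spread in postoperative pain may reflect how much pain patients report before surgery. A simple difference leaves that part in the error term. A linear model with the baseline score removes it, needs no new data and leaves the estimand (the mean difference between arms) unchanged. The interval is one of the pilot's stated criteria for a definitive trial, so its width matters. It also helps to fix the method before the data are seen: in so small a trial, choosing between an adjusted and an unadjusted interval afterwards could move the result across zero.

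**Working it through.** **Inputs.** From Sample Size: 240 procedures a year × 50% participation × 3/12 = 30 patients, hence n = 15 per arm at 1:1; difference 1; SD 1.2. From Statistical Analysis: an 80% interval, read as two-sided (10% in each tail). Assumed, because the protocol gives no value: R², the share of variance in 24-hour average NRS that the covariate explains within arm, over 0 to 0.3.

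**Step 1: reproduce the plan's figure.**
- SE = 1.2 × √(2/15) = 0.438.
- Critical value t(0.90; 28 df) = 1.3125; half-width = 1.3125 × 0.438 = 0.575.
- Noncentrality = 1/0.438 = 2.282. The noncentral t gives a probability of **83.3%** that the interval excludes 0 in favour of LA block (84.1% by normal approximation).
- The stated figure of more than 80% is confirmed without adjustment.

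**Step 2: one covariate.** The residual SD becomes 1.2 × √(1 − R²). Estimating k covariate slopes costs k degrees of freedom and, because covariates are never perfectly balanced between arms, inflates the variance of the arm effect on average by 1 + k/(2n − k − 3). For k = 1 this is 1 + 1/26 = 1.038, with 27 df and critical value 1.3137. For R² = 0.1: SD = 1.138, SE = 1.138 × √(2/15 × 1.038) = 0.424, half-width = 0.557.

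| Assumed R² | Half-width | Change from 0.575 | Probability of excluding 0 |
|---|---|---|---|
| 0 | 0.587 | 2% wider | 82.2% |
| 0.04 | 0.575 | none | 83.4% |
| 0.1 | 0.557 | 3% narrower | 85.1% |
| 0.2 | 0.525 | 9% narrower | 88.2% |
| 0.3 | 0.491 | 15% narrower | 91.2% |

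Break-even is near R² = 0.04, a correlation of 0.2. A simulation with one normally distributed covariate (60,000 trials per setting) agreed: 82.3%, 83.4%, 85.1%, 88.1% and 91.2%.

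**Step 3: why only one covariate.** For k = 4 the inflation is 1 + 4/23 = 1.174, with 24 df and critical value 1.3178.

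| Assumed R² (all four together) | Half-width | Probability of excluding 0 |
|---|---|---|
| 0 | 0.626 | 78.5% |
| 0.1 | 0.594 | 81.6% |
| 0.15 | 0.577 | 83.2% |
| 0.2 | 0.560 | 84.9% |
| 0.3 | 0.524 | 88.3% |

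Four useless covariates cost about 5 points (83.3 − 78.5 = 4.8), and below an R² of about 0.15 the interval is wider than the unadjusted one. Leaving out the inflation term would hide this cost.

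**The case against.** The strongest objection is that the protocol never says the interval is unadjusted. An ANCOVA coefficient is also a between-group difference, and covariate choice is often left to a statistical analysis plan, which may exist here. That stands to this extent: adjustment is not excluded, and nothing in the protocol is wrong or contradictory on the point. But the only analysis stated is a difference, sized on a raw SD, and the interval feeds a criterion that the protocol itself fixes. The protocol is a reasonable place to settle it.

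A second objection is that the benefit is unproven. The protocol gives no correlation between preoperative and 24-hour NRS. If most patients report little or no pain before surgery, the correlation could be near zero. That also stands, and it is why the gain is shown as a range. What can be said is that the possible loss is about one point.

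A reader might infer more than the protocol supports:

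- **That surgical factors should be adjusted for too, because the protocol names them as pain drivers.** The Introduction lists axillary surgery as a risk factor for chronic pain, and what it says of expanders is that "the use of tissue expanders increases the use of opioid and non-opioid analgesia", which concerns analgesic use and not NRS. Patients having a symmetrising procedure "will not have a regional block on the symmetrizing side", so pain from that side could enter the score, but the protocol does not say that it raises it. Step 3 shows the price of a larger model.
- **That planned-procedure values are already on file.** The Data Collection section records the surgery performed ("tissue expander or immediate implant reconstruction; adjunctive procedures will be recorded including biopsies and balancing reduction procedures"). It lists no planned-procedure field, and the surgery follows randomisation.
- **That chance imbalance makes the simple interval invalid.** It does not. The coverage of a randomised two-sample interval already allows for chance imbalance.
- **That this interval alone decides whether the definitive trial proceeds.** The protocol also sets three feasibility criteria and calls a favourable interval preliminary evidence only.

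**Conclusion.** The point holds as a minor improvement in efficiency. The efficacy interval is stated and sized as a simple difference, and a baseline value suited to adjustment is already collected. With 15 per arm, difference 1 and SD 1.2, adjusting for preoperative NRS alone takes the probability of excluding 0 from 83.3% to about 85%, 88% or 91% at an assumed R² of 0.1, 0.2 or 0.3, against about 82% at R² = 0. These figures assume a linear covariate effect, a common residual variance and complete data on 30 patients. The plan meets its own target of more than 80% unadjusted, so neither the sample size nor the validity of the stated interval is in question.

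**What to change.** Add to Statistical Analysis that the deciding 80% confidence interval is for the arm coefficient in a linear model (ANCOVA) of 24-hour average NRS on arm and preoperative NRS, with no other covariate. State that the baseline value is the one recorded before the block, and report the unadjusted interval alongside as supportive. Say likewise that any comparison of 24-hour QoR-15 is adjusted for baseline QoR-15; that outcome is outside the efficacy criterion, so this is for consistency.

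The cost is two sentences of text and no new data or patients. The statistical cost is one degree of freedom and about one percentage point in the probability of excluding 0 if preoperative NRS proves unrelated to the outcome. The sample size statement can stay as it is.

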24 hour time point will be marked on the QoR-15 form. If paper format is preferred, the QoR-15 will be provided with a paid-postage envelope to return once completed at 24 hours after surgery. The pain NRS at 24 hours will be recorded from the chart. The envelopes will be addressed to the research coordinator at UBC Hospital office. If the participant prefers electronic format, the questionnaire will be sent to their provided email address using secure online format (REDCap developed questionnaire).

Recovery Booklet (see Form 5) will include: a) schedule for taking prescription pain medications; b) a postoperative 7-day symptom diary (for recording pain on NRS at 24 hours, episodes of vomiting, nausea, and use of prescribed medications). Patients will be provided with a paid-postage envelope to return their Recovery Booklet via mail once completed at 7 days after surgery. Patients will be reminded to complete the Recovery Booklet (Form 5) in 3-4 days and once again at 14 days to return the envelope.

The Pain Burden Index questionnaire (see Form 8) asks specifically about pain in four surgically related body areas and to calculate the Pain Burden Index (PBI). The PBI is calculated by summing the pain severity scale (0–10) at each of four locations (breast, axilla, chest wall, arm) multiplied by the frequency of the pain at each site. The PBI questionnaire will be sent to participants via mail as paper format (with paid-postage envelope to return once completed) or email as electronic format (as per their requested preference) to be completed 3 and 6 months after their surgery. Details of present adjuvant treatments (radiation and chemotherapy) will also be included in the questionnaire.

Secondary outcomes data including opioid consumption and side effects, length of stay in hospital (hours), rescue medications, failure of early discharge, complications and adverse events and time-based outcome measures (time in PACU, time under general anesthesia, time to perform ultrasound-guided TPVB+, failure of discharge from PACU and requiring admission) will be collected through participants' charts and EMR.

Risk/Benefit Estimates [\(back\)](#)

Anticipated Benefits to Participants

Participants will be randomly assigned to receive TPVB+ nerve blocks with either local anesthetic or sham (saline) followed by general anesthesia.

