Participants who are randomly assigned to saline infiltration for TPVB+ may not notice any improvement in postoperative pain scores, opioid requirements, side effects related to opioid consumption (eg. nausea and vomiting), chronic pain, or shortening of hospital stay.

Participants who are randomly assigned to local anesthetic infiltration for TPVB+ may report reduced postoperative pain scores, require less total opioid analgesics or other medications in the perioperative period. Participants may experience fewer side effects

related to opioid consumption (eg. nausea and vomiting), may have lower risk of chronic pain, and may have shorter lengths of stay in hospital.

All participants will be asked to reflect on their recovery and pain when completing the QoR-15 and PBI questionnaires. If appropriate, any issues flagged through completion of the QoR-15 or PBI questionnaire may be addressed to optimize participant recovery and optimize chronic pain control.

Potential Harms or Risks to Participants

Participants randomly assigned to the sham or local anesthetic TPVB+ followed by general anesthesia will be exposed to risks associated with the administration of regional blocks, such as (but not limited to) pain or discomfort at the time of the injection, hematoma, or pneumothorax.

Adverse events from the TPVB have been reported in meta-analyses of randomized clinical trials. Failed anesthetic technique was the most common adverse event reported with a relative risk of 4.34 (CI 0.74 - 25.24).²⁹ Other adverse events were rare with low relative risks: pneumothorax (RR 0.01, CI 0.02 – 0.03, occurs in 1 in 600 cases); post-operative nausea and vomiting (RR 0.26, CI 0.13 – 0.5); nerve damage (n=0), and vascular injury (n=0).²⁹ Horner's syndrome (sympathetic blockade) has occurred in less than 1 in 100 cases.²⁹ Nerve damage and vascular injury have a theoretical risk of 1 in over 1000 cases.²⁹ Local infection has a theoretical risk of 1 in 2500 cases.⁷¹ Horner's syndrome (temporary small pupil and droopy eyelid) has occurred in less than 1 of 100 cases.²⁹

Participants receiving the saline TPVB+ may not experience improved pain scores or reduced opioid consumption postoperatively, unlike what is expected for participants receiving a local anesthetic regional block.

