Data collected on the day of the surgery (Clinical Form: 6) will be directly inserted into REDCap web application. Should any unforeseen circumstance make direct data entry unavailable on the day of surgery, hard copies of Form 6 will be used as a backup. This will also be stored in a locked secured filing cabinet in the PI's office

The Pain Burden Index questionnaire (Form 8) will be given to participants and completed at 3 and 6 months after surgery. The patient will receive the questionnaire 1 week before each of these dates and receive a phone call from the Research assistant to ensure receipt and answer any questions. The completed Pain Burden Index questionnaire will be stored with the other hard-copy study forms in a locked secured filing cabinet in the PI's office. If the patient prefers emailed questionnaires, the questionnaire will be completed using a secure online survey format and anonymized to their assigned study ID number.

The Data Collection Form outlines the variables and unit measures for the study and will not be used to store any data. Instead, participants' data from the Intake Form, Clinical Form, Quality of Recovery-15 Questionnaire, Recovery Booklet, Clinical Form and Pain Burden Index will be collected and entered into the REDCap server directly through a password-protected encrypted laptop. No identifying information will be stored on REDCap except for email of the patients who have opted for electronic surveys.

In summary, the Informed Consent, Intake Form, Clinical Form, Quality of Recovery-15 Questionnaire, Recovery Booklet, and Pain Burden Index will be kept as hard copies in the PI's office in a locked secured filing cabinet, separate from the Code Break linking list. Study Data Log and the Recruitment Log will be stored on the UBC server. All non-identifying data collected will be stored on REDCap. Since the Code Break is stored separately from clinical data collected on REDCap, there is minimal risk of linking participants' identifying information.

	Personal Identifying Information	Storage		
		Hard-Copy*	REDCap	Encrypted MS Excel Sheet†
Informed Consent Form (Form 2)	x	x		
Intake Form (Form 4)		x	x	
Recovery Booklet (Form 5)		x	x	
Clinical Form (Form 6)		x	x	
Quality of Recovery-15 Questionnaire (Form 7)		x	x	
Pain Burden Index (Form 8)		x	x	
Recruitment Log (Form 9)				x
Code Break (Form 10)	x			x
Study Data Log (Form 12)				x

[figure not shown]
* Stored in Locked Cabinet in PI Office

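### The only described form field for block and surgical complications stops at 24 hours, while the pilot's adverse event outcome and the other recording rules carry no such limit

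*Protocol*

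**What the plan says.** The Data Collection section of the protocol lists the data for all participants in seven form-based items. Only item 3, the second section of the Clinical Form, mentions complications: "Surgical and regional block complications within 24 hours of surgery will be recorded".

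Other sections treat the same data without that limit:

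- Outcome Measures: "Secondary outcomes of the pilot trial include adverse events related to study interventions". No window is given. The section adds: "We will also collect the outcomes for the definitive trial to test and refine data collection processes".
- Outcome Measures, complications and adverse events: the block-related list starts with vascular or nerve injury, Horner's syndrome and bleeding or hematoma, and ends "local anesthetic systemic toxicity, pneumothorax, distortion tissue planes during axillary dissection, and other". It has no window. The surgical list reads "hematoma, tissue necrosis, urgent unplanned return to the operative theater within 24 hours of surgery", where the 24 hours may qualify the last item or all three.
- Additional Details of Study Design: complications and adverse events come from the chart and electronic record, with no cut-off.
- Adverse Events: events related to the block are tracked on REDCap according to the Data Collection Form, with no cut-off.
- Confidentiality: the Data Collection Form only defines variables and holds no data. Entries come from the Intake Form, Clinical Form, QoR-15, Recovery Booklet and Pain Burden Index.

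The risk section also discloses infection: "Local infection has a theoretical risk of 1 in 2500 cases".

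**The concern.** An adverse event outcome needs a defined period and a place to record the event. Here the outcome is open-ended, but the one described field closes at 24 hours. The protocol itself expects some patients to be home by then, because it counts opioids taken at home within 24 hours of surgery.

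Some listed or disclosed block harms could plausibly first be noted after that point: nerve injury, hematoma, pneumothorax, or infection under the open category. If they have no field, the count in either arm can be too low, and a reader of the results could not tell no event from not asked. This matters in the sham arm too, since the protocol says that sham participants are exposed to the risks of the block procedure and may see no improvement in pain.

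The pilot shares its design with the definitive trial and is meant to test data collection, so an unclear window would be carried forward.

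**Working it through.** **1. Does an untimed route restore later capture?**

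- Adverse events rule: it points to the Data Collection Form. Confidentiality says that form holds no data and that entries come from five other forms. Of these, only the Clinical Form is described as recording complications, and Confidentiality describes it as data collected on the day of surgery. This route leads back to the 24-hour field.
- Chart and electronic record: no cut-off is stated, so later events could be found here. However, Data Collection describes chart collection on the day of surgery, with the electronic record used if required. No later review is scheduled.
- Emergency visits: counted to 48 hours after discharge. This catches only events that lead to such a visit.
- Recovery Booklet (7 days): described as covering medications, nausea and vomiting, and 24-hour pain.
- Pain Burden Index (3 and 6 months): described as covering pain at four sites and adjuvant treatment. A painful late effect might show as pain, but not as a complication.

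So no described form field takes a block complication first noted after 24 hours. The chart and the emergency-visit count are partial routes.

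**2. How much could it change the counts?**

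The plan states no figure for this point, so there is none to reproduce. Inputs:

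- n = 30. Sample Size gives 240 procedures a year and 50% participation: 240 / 4 × 0.5 = 30 in three months. Allocation is 1:1, so 15 per arm.
- r = 0.70%, the complication rate that the Introduction quotes for ultrasound-guided paravertebral block. Applying it to all 30 is a simplification, because sham saline is placed outside the paravertebral space and the intervention adds a Pecs I block.
- L = share of events first noted after 24 hours and then missed. This is not in the documents, so it is assumed and varied.

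Expected events: 30 × 0.007 = 0.21.

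Chance of recording at least one: 1 − (1 − r(1 − L))^n.

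| L (assumed) | n = 30 |
|---|---|
| 0 | 1 − 0.993^30 = 19.0% |
| 10% | 17.3% |
| 25% | 14.6% |
| 50% | 1 − 0.9965^30 = 10.0% |
| 75% | 5.1% |

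For the 15 patients in the active arm, the chance is 10.0% with L = 0 and 5.1% with L = 50%. For infection at 1 in 2500, 30 patients give 30 / 2500 = 0.012 expected cases. Even with complete capture, no events in 30 patients leaves a one-sided 95% upper bound of 1 − 0.05^(1/30) = 9.5%.

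**3. The definitive trial**

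With about 220 patients, the active arm has about 110. At 0.70%, the chance of recording at least one event is 1 − 0.993^110 = 54% with L = 0 and 1 − 0.9965^110 = 32% with L = 50%.

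**The case against.** The strongest reply is that the protocol never says complications are recorded only for 24 hours. Item 3 describes one section of one form. Chart and electronic record collection has no cut-off, adverse events are tracked on REDCap without one, and the Recovery Booklet, Clinical Form, Pain Burden Index and Data Collection Form are attached by reference but not shown. Any of them might ask about complications later. This stands in part: it cannot be said that later harms are certainly missed. But if a form does run longer, it contradicts item 3, and the text still has to be reconciled.

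A second reply is that late onset is a clinical inference. That stands: the documents give no onset times.

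A third is that the numbers are too small to matter. That stands for the pilot. With 0.21 expected events, it can say little about block safety under any window.

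A reader might also go further in two ways that the documents do not support:

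- That late tissue necrosis is lost from the pilot's named secondary outcome. That outcome covers events related to the study intervention, which is the block. Necrosis is in the surgical list of the definitive trial, which the pilot collects to test its processes.
- That the pilot's safety count decides whether the definitive trial goes ahead. The progression criteria are enrolment, block success, six-month retention and an 80% confidence interval for pain. No harm count is among them.

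**Conclusion.** The sections conflict, and they should be reconciled. A stated 24-hour limit governs the only described field for complications, while the outcome it should serve, the block-harm list and two recording rules have no limit. Followed as written, block-related harms first noted after 24 hours may be under-recorded in both arms, except those noted in the chart or electronic record or leading to an emergency visit within 48 hours of discharge.

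The effect on pilot counts is small: the chance of recording any event falls from 19% to 10% if half of events arise after 24 hours and are missed. This rests on the protocol's 0.70% rate applied to all 30 blocks and on an assumed late share. The greater weight lies in settling the process before it is carried into about 220 patients. A reader might infer that harms are certain to be missed or that the pilot's safety result will mislead. The documents support only that the count may be biased low.

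**What to change.** Replace the 24-hour limit in item 3 of Data Collection with two statements: one window and source for block-related adverse events, and one for surgical complications, both running beyond 24 hours. Keep the 24-hour count as a separate row. Say whether the 24 hours in the surgical list applies to all three items or only to the return to theatre.

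Use contacts already planned, with one or two complication questions added. These are the 7-day Recovery Booklet, its reminders at 3 to 4 days and "once again at 14 days to return the envelope", and the contacts around the 3- and 6-month questionnaires, when patients "receive a phone call from the Research assistant to ensure receipt and answer any questions". The protocol does not say how the booklet reminders are made, so if they are not calls the questions can go in the booklet itself.

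Then align Outcome Measures, Additional Details of Study Design, Adverse Events, Data Collection and Confidentiality with those windows, and name the form that stores adverse events.

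The cost is a small amendment, one or two extra questions per contact, and a few more adverse event records to classify. Sample size, randomization and the primary analysis do not change.
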